A randomized-controlled trial comparing liposomal bupivacaine, plain bupivacaine, and the mixture of liposomal bupivacaine and plain bupivacaine in transversus abdominus plane block for postoperative analgesia for open abdominal hysterectomies

Clinical Trials registration number: NCT03250507

Document date: 6/22/2016

HENRY FORD HEALTH SYSTEM IRB PROTOCOL FORMAT

Appendix 1

(Incomplete applications will be returned, & inadequate responses may lead to a delay in review.) You may mark your responses in the shaded areas following each question. Supporting documents (articles, drug toxicity information, etc.) must be submitted when applicable. A "See Attached" response will not be accepted for review. Be concise & clear.

Directions:

Sponsored protocol: If you have a sponsored protocol (e.g., pharmaceutical), a grant application (e.g., National Institutes of Health), or another peer-reviewed protocol, you may submit that protocol/application along with the application elements. It is the responsibility of the Principal Investigator to assure, however, that the protocol/application contains the information requested in this "IRB Protocol Format". Additional sheets should be attached to the protocol/application as necessary to provide the information (e.g., a description of the process of consent) required for IRB review. When available, the Investigator's Brochure must be submitted along with the research protocol, or a summary of the preclinical/animal data and any relevant clinical data.

Physician Initiated protocol: If you have not been provided a protocol from an outside source, you must develop one. The following is the "Henry Ford Health System "IRB Protocol Format".

1. PURPOSE: State in one or two sentences the purpose or objective of this project. The goal of this study is to evaluate the effectiveness of different formulations of bupivacaine infiltrated into the transversus abdominis plane (TAP) on post-operative pain management after open abdominal hysterectomy.
2. SPECIFIC AIMS: Number your aims so that the aims can be referred to in the Project Design and Data Analysis sections of this outline. 1) To determine if a TAP block with liposomal bupivacaine provides effective post-operative analgesia after open abdominal hysterectomy. 2) To determine if the mixing of liposomal bupivacaine with bupivacaine hydrochloride provides improved analgesia as compared to either drug alone when used for a TAP block.
3. RATIONALE FOR THE PROJECT:
 - a. State the rationale for the project and support it with background information about the project. Critically evaluate existing knowledge, and specifically identify the gaps in knowledge the project will fill. Liposomal bupivacaine is a novel formulation of the local anesthetic bupivacaine in which the drug is encapsulated and slowly released over time up until 72 hours post-injection. Since liposomal bupivacaine is slow-released, liposomal bupivacaine may provide delayed post-operative analgesia. Bupivacaine hydrochloride typically provides 24-48 hours of analgesia. We hypothesize that the combination of liposomal bupivacaine to bupivacaine hydrochloride will provide superior analgesia both immediately and up to 72 hours post-operatively. Liposomal bupivacaine was initially FDA approved for surgical site infiltration and has been recently FDA approved for infiltration in the transversus abdominus plane. TAP blocks are routinely used as a part of multimodal analgesia to decrease pain scores and decrease opioid consumption after abdominal surgery. Liposomal bupivacaine infiltrated into the TAP plane has been shown to be effective for post-operative analgesia after robotic prostatectomy, laparoscopic colorectal surgery, and abdominal hernia repair; however, those studies did not compare the effectiveness of liposomal bupivacaine to bupivacaine hydrochloride or to the mixture of Liposomal Bupivacaine and Bupivacaine HCL. Our experience at Henry Ford Hospital suggests that TAP blocks with liposomal bupivacaine provides similar analgesia as those with bupivacaine hydrochloride. This year, a randomized controlled single blinded study comparing liposomal bupivacaine to bupivacaine hydrochloride for TAP blocks for patients undergoing laparoscopic assisted donor nephrectomy showed no difference in pain scores or opioid consumption within the first 48 hours post-operatively. Opioid consumption was slightly decreased 48-72 hours post-operatively in the liposomal bupivacaine group.
 - b. State the applicant's prior research and experience in this research area. As a quality improvement initiative, we have retrospectively reviewed the effectiveness of TAP blocks with liposomal bupivacaine and bupivacaine hydrochloride for post-operative analgesia after laparoscopic assisted colectomy and open abdominal hysterectomy. As members of the regional anesthesia division, we have extensive experience performing TAP blocks for a wide range of abdominal surgical procedures.
4. SIGNIFICANCE: State concisely the importance of this project by relating the purpose to broader, long-range objectives. Providing optimal post-operative analgesia to our patients is important to improve

patient satisfaction, decrease opioid related side effects, and promote early recovery and discharge from the hospital. This study will help determine if using liposomal bupivacaine alone or in combination with bupivacaine hydrochloride provides enhanced post-operative analgesia.

5. SUBJECTS IN THE PROJECT:

- a. State the inclusion and exclusion criteria for enrollment of subjects. Inclusion criteria: elective open abdominal hysterectomy with a midline incision, age>18, ASA 1-3. Exclusion criteria: patient with a chronic pain condition, major unexpected surgical complication, unexpected prolonged intubation, patient refusal, local anesthetic allergy, any contraindication to regional anesthesia, and greater than two attempts for TAP block by residents and greater than one attempt by staff anesthesiologist.
- b. Describe the control population (if utilized) and justify its selection. Our current standard practice is to use 0.25% bupivacaine for TAP blocks, therefore, the control population is the group receiving 0.25% Bupivacaine.
- c. Support the likelihood of recruiting the number of subjects required to complete the project. Relate this to other projects recruiting similar subjects. We estimate that 100-150 patients undergo open abdominal hysterectomy with a midline incision at Henry Ford Hospital each year. We anticipate an 80% or higher recruitment rate. Therefore, we anticipate recruiting 90 patients within a year. No other studies are recruiting similar patients.

6. PROJECT DESIGN AND PROTOCOL:

- a. Describe the experimental design/methodology. Prospective randomized observer-blinded controlled study.
- b. Outline the protocol, corresponding it to the specific aims; identify the data or endpoints to be analyzed to reach the specific aims. All eligible patients will be seen in the pre-operative holding area to discuss the study. Informed consent will be obtained at that time. The patient will be randomized to one of three groups by random envelope selection. Group 1 will receive a TAP block with a total of 60 mL 0.25% bupivacaine hydrochloride. Group 2 will receive a TAP block with a total of 20 mL of liposomal bupivacaine and 40 mL normal saline. Group 3 will receive a TAP block with a total of 20 mL of liposomal bupivacaine and 40 mL 0.25% bupivacaine hydrochloride. Our standard sedation protocol for all patients receiving any nerve block is to provide a maximum of 2 mg midazolam and 100 mcg fentanyl during procedure. The patient will be monitored per our routine practice standards. The patients will undergo the surgical procedure with general anesthesia as directed by the attending anesthesiologist. All patients will receive 30 mg ketorolac IV. If ketorolac is contraindication, the patient will receive 1000 mg acetaminophen IV. The patient will be recovered and receive routine post-operative care. Patients will be assessed immediately post-operatively in the post-anesthesia care unit (PACU), and one time during each of the following time periods: 0-24 hrs post-operatively, 25-48 hours post-operatively, and 49-72 hours post-operatively. Primary outcomes are total opioid consumption, time to the first opioid administration, and pain score during the above mentioned time periods. Secondary outcomes are patient satisfaction, length of stay in hospital, timing of ambulation, presence of nausea and vomiting, evidence of local anesthetic toxicity and any postoperative hemodynamic instability.
- c. Discuss potential limitations and difficulties in the protocol. We don't anticipate any difficulties with this protocol since patients typically receive a TAP block for post-operative analgesia for open abdominal hysterectomy at Henry Ford Hospital. One limitation of our protocol is that it is not double-blinded. Liposomal bupivacaine is white and distinctive from bupivacaine hydrochloride. Therefore, the anesthesiologist performing the block cannot be blinded to group selection. All other care team members including anesthesia team, surgical team, and floor nurses, will be blinded to the group selection.
- d. Provide a tentative schedule for conducting and completing this project and, if applicable, the multicenter study. We anticipate one year to recruit patients and collect data. Data analysis will take a few months after study completion.
- e. **Data collection:** Submit a copy of the data collection tool or list the data fields to be collected (review IRB policy, Access to Medical Records for Research). Age, ASA classification, height, weight, BMI, indication for hysterectomy, surgeon, duration of surgery, time of TAP block, time to first break-through analgesic, cumulative analgesic doses and pain scores at rest and with movement in PACU and in the following time periods: 0-24 hours, 25-48 hours, 49-72 hours. in 6 hr increments for the first 24hrs, then every 12 hrs for the next 24 hours. Satisfaction (ie not satisfied, satisfied, very satisfied), length of stay in the hospital, presence of ambulation, presence of nausea and vomiting, evidence of local anesthetic toxicity, presence of hypotension.

7. DATA ANALYSIS: Describe the analysis of the data and relate this to the specific aims in detail. Case reports and medical record reviews also require a description of the planned data analysis (ie. descriptive, observational). The Committee recommends free consultation with the Division of Biostatistics and Research Epidemiology before IRB submission. Many clinical measurements will be recorded post operation. Some are one-time measurements such as total opioid consumption, and some are repeated measurements such as pain scores. Total 8-9 measuring times for those

repeated outcomes. Ideally these time points are at baseline, 6 hours, 12 hours, 18 hours, 24 hours, 36 hours, 48 hours, 60 hours and 72 hours. Continuous variables will be summarized with n, mean, standard deviation and range. Frequency counts and percentage will be provided for categorical data. Estimates for averages and proportions will also include 95 % confidence intervals. One-way Analysis of Variance(ANOVA) will be used to assess the efficacy of three anesthetic bupivacaine formulas (G1: bupivacaine HCL; G2: liposomal bupivacaine ; G3: liposomal bupivacaine + bupivacaine HCL) on total opioid consumption, patient satisfaction, length of stay in hospital as well as timing of ambulation. Generalized Estimating Equations (GEE) will be utilized to evaluate the effects of these three anesthetic formulas on repeated measures of pain scores, presence of nausea and vomiting, evidence of local anesthetic toxicity and any postoperative hemodynamic instability. Cox proportion hazard models will be applied to assess the effect of these anesthetic formulas on the time to first opioid administration. The statistical analysis will be obtained by using SAS 9.4 and the tests are claimed to be significant if the p- values are less than 0.05.

8. JUSTIFICATION FOR NUMBER OF SUBJECTS OR DATA:

- a. State the number of subjects or data points to be analyzed in the project at this institution and the total number for multicenter studies. The Committee recommends consultation with the Division of Biostatistics and Research Epidemiology [contact]. Total 90 subjects are expected given at least 80% recruitment rate of total 100-150 patients undergo open abdominal hysterectomy at Henry Ford Hospital each year.
- b. Describe the statistical justification for this number of subjects or data points. Total 90 patients (30 for each of these 3 groups) will have 80% power to detect the effect size of 0.33 by using One- Way ANOVA for assessing the effects of three formulas on total opioid consumption; and an effect size of 0.24 can be detected with 80% power assuming 0.5 correlation among repeated measures by using repeated One - Way ANOVA for assessing the effects of three formulas on pain scores.

FORM A

HENRY FORD HEALTH SYSTEM (IRB) DRUG/SUBSTANCE INFORMATION

(This form must be completed for each individual drug or substance -investigational or marketed- that is being administered as part of this research study)

1. Generic/Chemical Name: Liposomal Bupivacaine	2. Trade Name: Exparel
3. Manufacturer: Pacira Pharmaceuticals	4. Mode of Administration: other: infiltrated into the transversus abdominus plane
5. How Supplied (dose form & strength): 20 ML vials containing 266 mg liposomal bupivacaine.	6. Who will be administer the drug/substance? Staff anesthesiologist and resident anesthetist
7. Dosage and Schedule Proposed:Groups 2 and 3 will receive 20 mL liposomal bupivacaine as a one time injection for a TAP block.	
8. Will you be utilizing research pharmacy for storage or dispensing of any medication? (if this is an inpatient study, you are required to use research pharmacy).  Yes  No	
9. Describe the primary actions of the drug/substance:Sodium channel blocker that acts to block neuronal impulses.

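### Pre-operative opioid use is neither an explicit exclusion, a recorded field nor a covariate, although two of the three primary outcomes measure opioid use; the cost is precision, not bias.

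*Combined protocol and SAP*

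**What the plan says.** Section 6b sets the primary endpoints: "Primary outcomes are total opioid consumption, time to the first opioid administration, and pain score during the above mentioned time periods". Two of these three are opioid use itself.

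Section 5a admits patients as follows: "Inclusion criteria: elective open abdominal hysterectomy with a midline incision, age>18, ASA 1-3". The exclusions begin "Exclusion criteria: patient with a chronic pain condition, major unexpected surgical complication" and continue "unexpected prolonged intubation, patient refusal, local anesthetic allergy, any contraindication to regional anesthesia, and greater than two attempts for TAP block by residents". Neither list mentions current opioid use, tolerance or treatment for opioid dependence, and the chronic pain exclusion is not defined.

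The data fields in 6e open with "Age, ASA classification, height, weight, BMI, indication for hysterectomy, surgeon, duration of surgery, time of TAP block, time to first break-through analgesic". The analgesic doses that follow are post-operative: "cumulative analgesic doses and pain scores at rest and with movement in PACU and in the following time periods". No field covers opioids or other medication before surgery.

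For total consumption, section 7 says "One-way Analysis of Variance(ANOVA) will be used to assess the efficacy of three anesthetic bupivacaine formulas". It plans a Cox model for time to first opioid. No covariate is named for either model, and 6b allocates by envelope with no stratification stated.

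**The concern.** A chronic pain condition is a diagnosis, whereas opioid use is an exposure. The exclusion plausibly removes many long-term users. It does not name short-term use before surgery, or maintenance treatment in a patient without a pain diagnosis. Section 6e records the indication for hysterectomy, and 5a excludes no indication.

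Any such patient who enters is likely to use more opioid afterwards whichever block she receives. In arms of 30, that widens the spread of total consumption and lets an uneven split between arms move a mean by chance. Because prior use is not among the planned fields, the analyst could not show that the arms were balanced on it, or remove its contribution to the error variance. At stake is the precision of the opioid comparisons at a fixed N of 90.

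**Working it through.** **Inputs from the documents.** N = 90, 30 per arm; effect size 0.33, read as Cohen's f; 80% power; one-way ANOVA (8b); significance at 0.05 (section 7).

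**Inputs assumed, because the documents give none.** Share tolerant, p: 3%, 5% or 10% after the chronic pain exclusion. Extra opioid per tolerant patient, s: 2, 3 or 4 within-arm SD. The 0.33 is first taken as scaled to the SD of opioid-naive patients.

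**1. The plan's own figure.** Noncentrality = N × f² = 90 × 0.33² = 9.80. The noncentral F with 2 and 87 df gives power of 79.3%, and f for exactly 80% is 0.333. The stated 80% is reproduced.

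**2. Variance added by tolerant patients.** Within-arm variance is multiplied by VI = 1 + p(1 − p)s², so f becomes 0.33/√VI. Example with p = 5%, s = 3: VI = 1 + 0.05 × 0.95 × 9 = 1.4275; f = 0.33/1.195 = 0.276; power 63%.

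| Tolerant | s = 2 | s = 3 | s = 4 |
|---|---|---|---|
| 3% | 74% | 69% | 62% |
| 5% | 72% | 63% | 54% |
| 10% | 65% | 52% | 40% |

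Simulation at 5% and 10% (20,000 trials per setting) agrees within about one percentage point.

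**3. Adjustment.** In the same simulations, an analysis of covariance on a yes/no tolerance indicator (4,000 trials per setting) gave power of 78–79%. Type I error was between 4.4% and 5.6% with or without adjustment.

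**4. A harsher model.** Suppose opioid-naive patients have mean 60 and SD 36, and tolerant patients have three times both (all assumed). The variance is (1 − q)·36² + q·108² + q(1 − q)·120², with q the share tolerant. At 3%, 5% and 10% the SD is 45, 50 and 60. With f = 0.333 × 36/SD, unadjusted power is 60%, 50% and 36%. Adjustment removes only the last term and leaves 71%, 65% and 53%, so recovery is partial when tolerant patients are also more variable. If only the mean is tripled, unadjusted power is 67%, 61% and 49%.

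**5. Chance imbalance.** With equally spaced means, f = 0.33 is 0.33/√(2/3) = 0.40 SD between adjacent arms and 0.81 SD between the extremes. Each extra tolerant patient moves a 30-patient mean by s/30. One extra moves it 0.07 to 0.13 SD for s = 2 to 4, and two move it 0.13 to 0.27 SD. The probability that the highest and lowest arms differ by three or more tolerant patients is 12%, 27% and 51% at 3%, 5% and 10%.

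**6. The other reading of 0.33.** If 0.33 is scaled to the SD of the patients actually enrolled, their variance is already in it and step 2 does not apply: unadjusted power stays at about 80%. Adjustment then raises f to 0.33 × √VI. With p = 5% and s = 3 this is 0.33 × 1.195 = 0.394, and power on 2 and 86 df is about 92%.

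These figures concern total consumption only. No power was computed for the Cox model.

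**The case against.** An unadjusted comparison of randomised arms is valid, so this is a question of efficiency. That stands. A reader might go further and infer that a few tolerant patients could swamp an arm, or that the comparison is biased. The documents support neither. One or two extra patients at 2 to 4 SD move a mean by less than the 0.40 SD gap between adjacent arms, and matching that gap takes about three extra at 4 SD or four at 3 SD. An uneven split arises by chance, and the type I error stays near 5%.

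The power losses rest on assumed prevalence and dose shift, and on a reading of 0.33 that 8b does not state. This also stands, which is why both readings are shown. The chronic pain exclusion may leave very few such patients. At 3% there would be about three in 90, and a covariate resting on three patients achieves little.

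It is also tempting to say that tolerant patients could never be identified. That is true only of the listed fields; the documents do not say whether the medical record could supply the history later. But no such retrieval is planned, and a covariate chosen after outcomes are known is open to challenge. Indication and ASA class are recorded and may partly mark the group, but neither measures opioid use.

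**Conclusion.** The point holds as a low-priority improvement. Pre-operative opioid use is not explicitly excluded, not listed for collection and not adjusted for, while two primary outcomes depend on it. The consequence is lost precision and chance imbalance that cannot be checked.

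Its size cannot be fixed from the documents. It depends on three things they do not give: how many tolerant patients pass the chronic pain exclusion, how much more opioid they use, and which population's SD underlies 0.33. On the opioid-naive reading the loss runs from about 5 percentage points (3% tolerant, 2 SD) to about 39 (10%, 4 SD). On the enrolled-population reading nothing is lost from the stated 80%, and the plan forgoes a gain above it.

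**What to change.** Add one pre-operative item to 6e: opioid use in the weeks before surgery, as yes/no and daily dose. Complete it at the holding-area visit described in 6b, before the envelope is drawn, so that allocation cannot influence it. In section 7, prespecify the yes/no item as a covariate in the total-opioid model, which becomes an analysis of covariance, and in the Cox model for time to first opioid. Report the number of users by arm.

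The cost is one chart field and one degree of freedom. Eligibility, recruitment and N are unchanged. If few or no such patients enrol, there is little or no gain; if none do, the term drops out and the analysis reverts to the planned ANOVA.

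### Section 5a excludes patients for events that arise after randomisation, and no analysis population is named, so applying it removes randomised and mostly injected patients

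*Combined protocol and SAP*

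**What the plan says.** All references are to the combined protocol and SAP.

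- **5a** answers a form item that reads "State the inclusion and exclusion criteria for enrollment of subjects". Its exclusions include "major unexpected surgical complication, unexpected prolonged intubation" and "greater than two attempts for TAP block by residents and greater than one attempt by staff anesthesiologist".
- **6b** sets out the order: approach and consent in the pre-operative holding area, then "The patient will be randomized to one of three groups by random envelope selection", then the block, then surgery under general anesthesia. Its secondary outcomes include "evidence of local anesthetic toxicity and any postoperative hemodynamic instability".
- **6c** states that "the anesthesiologist performing the block cannot be blinded to group selection". It adds: "All other care team members including anesthesia team, surgical team, and floor nurses, will be blinded to the group selection".
- **Section 7** assigns ANOVA to total opioid consumption, GEE to repeated outcomes and a Cox model to time to first opioid. It does not say which patients enter these analyses.
- **Section 8b** claims 80% power at an effect size of 0.33 with 90 patients, 30 per group, and makes no allowance for loss.

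**The concern.** An exclusion criterion should be decidable before a patient is assigned. Two of these cannot be, and the third very probably is not. Because nothing else in the plan says how such patients are handled, the only written instruction is the one in 5a, which is to exclude.

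Two things are at stake. First, if removal depends on arm and the removed patients differ in outcome, the comparison of opioid use, time to first opioid and pain scores no longer rests on randomisation. The attempts criterion is the most exposed, because the person making the attempts knows what will be injected. Its wording also leaves room for judgement: the resident and staff limits are joined by a conjunction, and the text does not say whether a patient must exceed both or only one.

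Second, a patient with a major complication or prolonged intubation may be one in whom toxicity or hemodynamic instability occurs. Excluding that patient after injection thins the safety record even when the arms lose equal numbers.

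**Working it through.** **1. Timing.**

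| Criterion in 5a | Earliest point at which it can be known | Relative to the envelope (6b) |
|---|---|---|
| Major unexpected surgical complication | During surgery | After, with certainty |
| Unexpected prolonged intubation | End of surgery or later | After, with certainty |
| Too many block attempts | During the block | After, by sentence order; the text does not state when the envelope is opened relative to the first needle pass |

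**2. Analysis population.** Sections 7 and 8 give tests, summaries, software, a 0.05 threshold and a sample size. They contain no as-randomised or per-protocol definition, no rule for patients who meet 5a after randomisation, and no replacement rule.

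**3. The plan's own power figure.** For a one-way ANOVA with three groups, the noncentrality is f² × N with 2 and N − 3 degrees of freedom. With f = 0.33 and N = 90 it is 0.1089 × 90 = 9.80, which gives power of 79.3%. The stated 80% is reproduced to rounding.

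**4. Bias.** The documents give no rate for these events and no opioid SD, so the inputs are assumed. Let there be no true difference, 30 patients per arm, events at rate e in every arm, and an opioid excess of s for patients with an event (in SDs of the other patients). An arm that keeps such patients has its mean raised by e × s. An arm that removes them does not. If one arm alone removes them, it therefore looks better by e × s:

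| e | s | Bias (e × s) | ANOVA false-positive rate (simulated) |
|---|---|---|---|
| 5% | 1 to 1.5 | 0.050 to 0.075 SD | 5.3% to 5.6% |
| 10% | 1 to 1.5 | 0.10 to 0.15 SD | 6.3% to 7.4% |
| Same removal in all arms | 1 to 1.5 | 0 | 5.0% |

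The rates come from 200,000 simulated trials per row entry; repeating the simulation moved them by no more than 0.2 percentage points. For scale, the standard error of a two-arm difference is √(2/30) = 0.26 SD, so each of these biases is below one standard error.

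**5. Power if the patients are kept or dropped.** This takes 90 as the number randomised, with no replacement. Dropping leaves 90 × 0.95 ≈ 86 or 90 × 0.90 = 81, with noncentralities of 9.37 and 8.82. Keeping all 90 multiplies the variance by 1 + e(1 − e)s², so the noncentrality is 9.80 divided by that factor.

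| e | s | Variance factor | Noncentrality, keeping | Power keeping | Power dropping |
|---|---|---|---|---|---|
| 5% | 1 | 1.048 | 9.36 | 77.3% | 77.2% |
| 5% | 1.5 | 1.107 | 8.85 | 74.8% | 77.2% |
| 5% | 3 | 1.428 | 6.87 | 63.0% | 77.2% |
| 10% | 1 | 1.090 | 8.99 | 75.5% | 74.5% |
| 10% | 1.5 | 1.203 | 8.15 | 71.0% | 74.5% |
| 10% | 3 | 1.810 | 5.41 | 52.3% | 74.5% |

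These figures assume the drug difference is the same in the retained patients. If they showed none at all, f would also shrink by the factor 1 − e. At 10% events, power when keeping them would then be 65.8% (s = 1) or 61.2% (s = 1.5). That is a limiting case, since only the attempts criterion concerns difficult blocks.

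**The case against.** The strongest reply is that the plan is silent rather than wrong. Section 7 nowhere directs that anyone be dropped, and the enrollment wording in 5a is the form's printed prompt. That is fair as far as it goes. But the investigators themselves listed these events as exclusions, and since they cannot operate at enrollment, the only way to follow them is to remove patients later.

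Several limits on the point stand:

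- **Attempts timing.** Certainty that all three events follow the envelope is not available. For attempts, the order in 6b and the operator's need to know what to inject make it the natural reading, no more.
- **Route to bias.** Under 6c the complication and intubation events would probably be judged by blinded staff, so attempts are the main route to removal that depends on arm. If attempts alone accounted for an assumed 1-3% in one arm, the bias would be about 0.01-0.045 SD and the false-positive rate 5.0-5.2%.
- **Large inflation.** A reader might infer a serious excess of false positives. A rate of 9.4-14.0% does appear if 20% are removed from one arm only, but nothing in the documents supports such a scenario.
- **The meaning of 90.** A reader might also infer a contradiction over whether 90 are randomised or analysed. That rests on a printed prompt in 8a. The investigators' own words concern recruitment, as in 5c: "Therefore, we anticipate recruiting 90 patients within a year". What remains is that 8b allows for no loss.
- **Power.** Keeping everyone can cost power, and with a large opioid excess the cost is not small.

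**Conclusion.** The point holds, and should be fixed before any data are seen. That 5a conflicts with the sequence in 6b, and that no analysis population is named, is plain from the text. The consequence is conditional. Bias needs removal that differs by arm and relates to outcome; equal removal of similar patients gives none. Under the assumed 5-10% removal in one arm and a 1-1.5 SD excess, it is about 0.05-0.15 SD, with a false-positive rate of about 5-7%. Neither size nor direction can be derived from the documents. The possible loss of injected patients from the toxicity and hemodynamic outcomes does not depend on those assumptions about arms.

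The case rests on protecting the randomised comparison and the safety record. It does not rest on power, and it says nothing against any clinical limit in the plan.

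**What to change.** 1. In 5a, separate the criteria that can be known before the envelope is opened from the events that come later. The investigators should reconcile the wording and status of the attempts criterion, stating whether both limits or either one is meant. No clinical limit needs to change, and where the text belongs is for them to decide.
2. In Section 7, define the primary analysis as all randomised patients in their assigned group, with outcome data collected for all of them as far as possible. Report toxicity and hemodynamic outcomes for everyone who received any study injection.
3. Report the three events, and the number of missing pain scores, by arm.
4. Present the analysis that excludes these patients only as a sensitivity analysis.

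The cost is a few sentences, a record of the three events, and follow-up of the affected patients (about 5 to 9 of 90 at an assumed 5-10%). The downsides are more spread in opioid totals, some missing pain scores and some dilution. Power may fall below the stated 80%, by an amount that depends on the assumed event rate and opioid excess. The change does not make the numbers randomised and analysed identical: withdrawals, cancelled operations and missing outcomes remain. Section 7 would still need to say how missing pain scores are handled and how time to first opioid is counted in patients who stay intubated.

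### Three unranked primary outcomes are each tested at p<0.05 with no rule for combining them; if any one success counts, the chance of a false primary claim is up to about 14%

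*Combined protocol and SAP*

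**What the plan says.** Section 6b lists the outcomes in one sentence: "Primary outcomes are total opioid consumption, time to the first opioid administration, and pain score during the above mentioned time periods". It does not rank them.

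Section 7 assigns a model to each: one-way ANOVA for total opioid consumption, GEE for the repeated pain scores, and for the third, "Cox proportion hazard models will be applied to assess the effect of these anesthetic formulas on the time to first opioid administration". One criterion covers every analysis: "the tests are claimed to be significant if the p- values are less than 0.05".

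Section 8b bases the 90 patients (30 per group) on two of the three. For opioid consumption the trial "will have 80% power to detect the effect size of 0.33". For pain, "an effect size of 0.24 can be detected with 80% power assuming 0.5 correlation among repeated measures". Time to first opioid has no power statement, and section 8b calls none of the outcomes decisive.

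No section gives a testing order, a multiplicity adjustment, or a statement that one, some or all of the three must be significant.

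**The concern.** The outcomes, models and threshold are fixed in advance. What is left open is how three results combine into an answer to the aims. Suppose opioid consumption differs between groups and pain does not, or only time to first opioid differs. The plan gives no pre-set interpretation of either pattern, so the choice can be made after the results are seen.

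The readings differ in error rate. If any one of three tests at 0.05 is enough, chance alone gives a primary claim more often than 5% of the time. If all three are needed, it does so at most 5% of the time. A reader of the final report could not tell from the plan which rule had been meant.

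**Working it through.** **Inputs from the documents.** Three primary outcomes (section 6b); 0.05 per test (section 7); three groups of 30, N = 90, effect size f = 0.33 for opioid consumption, f = 0.24 for pain with correlation 0.5 among repeated measures (section 8b).

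**Assumed input.** The correlation between the three outcomes is not given; the 0.5 in section 8b is within patients across time for pain. A range of 0 to 0.9 is shown.

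**1. The plan's own figure.** One-way ANOVA, 2 and 87 degrees of freedom, noncentrality N × f² = 90 × 0.33² = 9.80. Power at 0.05 is 79.3%, which agrees with the stated 80%.

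**2. Any one success counts, independent outcomes, all nulls true.** 1 − (1 − 0.05)³ = 1 − 0.8574 = 14.3%. Whatever the dependence, the sum 3 × 0.05 = 15% is an upper bound.

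**3. Any one success counts, correlated outcomes.** Simulated null trials (3 × 30 patients, three equally correlated normal outcomes, one overall F test each at 0.05, 200,000 trials per setting):

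| Assumed correlation | At least one significant |
|---|---|
| 0 | 14.2% |
| 0.3 | 13.8% |
| 0.5 | 12.7% |
| 0.7 | 11.3% |
| 0.8 | 10.0% |
| 0.9 | 8.6% |

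Normal outcomes with F tests stand in for the planned GEE and Cox models. This isolates the effect of testing three outcomes from any small-sample error of the individual tests.

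**4. All three must succeed.** The claim is false only if a test with a true null is significant, so the rate cannot exceed that test's 5%. With all nulls true it was about 2% or less in the simulation.

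**5. Power under possible rules.**
- Opioid consumption at 0.05: 79.3%. At the Bonferroni level 0.05/3 = 0.0167: 64.4%.
- Pain tested alone: noncentrality N × f² × m / (1 + (m − 1) × 0.5), where m is the number of assessments. With m = 9 (the time points in section 7): 90 × 0.0576 × 9/5 = 9.33, power 77.1%. With m = 4 (PACU plus three periods, section 6b): 90 × 0.0576 × 4/2.5 = 8.29, power 71.8%. Both are below the 80% in section 8b, which does not say which formula was used.
- Pain second, after opioid consumption: both tests must be significant. If the outcomes are independent, 0.793 × 0.771 = 61% with nine assessments and 0.793 × 0.718 = 57% with four. Positive correlation raises these figures, but they cannot exceed pain's stand-alone power.

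**The case against.** The strongest reply is that the plan never promises a single verdict or an overall 5% error rate. The three outcomes are named beforehand, each has a model, and estimates carry 95% confidence intervals. If each is read as its own question, whether to adjust is partly convention. This stands in part: a reader might infer that the plan breaks a promise of 5% overall control, but it makes none. It does call all three outcomes primary and attach one significance criterion to each, without saying how they answer the aims together.

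A second reply is that opioid consumption is implicitly first, because it is listed first and powered first. List order is not a testing rule, and section 8b claims 80% power for pain as well.

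A third is that 14.3% describes an unlikely case, since pain and opioid use are related. That is fair: 14.3% is near the top of the range for one test per outcome. At an assumed correlation of 0.9 the figure is still about 9%.

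On the other side, a reader might infer an error rate above 14% from other sources of multiplicity: pain at rest and with movement (section 6e), the number of pain assessments, or the contrasts in Aim 2. The documents do not say that each of these is a separate primary test, so they are kept out of the figure.

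Finally, a fixed order is not the only remedy. An all-must-succeed rule or an adjusted threshold would also close the gap. The defect is that no rule is stated.

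**Conclusion.** The concern holds as a missing decision rule, and it should be fixed. If any one success counts, the chance of at least one false primary claim is up to about 14%: 14.3% under independence, about 9% at an assumed correlation of 0.9. If all three must succeed, it is at most 5%. These figures assume one overall three-group test per outcome, each holding its own 5% level, and all nulls true for the any-one figures.

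A reader might infer that the trial's false-positive rate is 14.3%. The documents do not support that: they adopt neither the any-one-success reading nor independence. They simply do not exclude that reading. The absence of a rule is certain from the text; the size depends on an unstated correlation.

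**What to change.** Amend sections 6b and 7 before any outcome is examined by group. Timing the change as before unblinding would not work, because section 6c says "the anesthesiologist performing the block cannot be blinded to group selection".

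The amendment should:
- name one primary outcome, tested at 0.05;
- place the other two in a fixed order, each tested at 0.05 only if the one before it is significant, and otherwise reported as estimates with 95% confidence intervals;
- define the pain outcome that takes a place in the order, since section 6e collects "pain scores at rest and with movement in PACU" and in later periods.

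The investigators should choose and justify the order. Total opioid consumption and pain have power calculations; time to first opioid has none, so its own power cannot be stated from the documents.

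**Cost.** No extra patients, and no power loss for the first overall test: 79% for opioid consumption at f = 0.33, against 64% under Bonferroni. This says nothing about power for the Aim 2 contrasts.

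**Downside.** The second and third outcomes lose confirmatory power. With opioid consumption first, any second outcome is capped at about 79%. Pain in second place falls below its stand-alone 77% (nine assessments) or 72% (four), to as little as 61% or 57% if the two outcomes are independent. An isolated result on a later outcome becomes supportive only.
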